9.5 Accounting procedures for missing, non-assessable and equivocal data

Missing, non-assessable and equivocal data will not be substituted and considered to the frames of statistical analysis of the results. All missing or equivocal data as well as data, not included into statistical analysis, will be registered according to CRO procedures. All data unaccounted during analysis will be described and justified in final study report.

Before taking decision concerning inclusion of data, obtained during clinical study, into assessment, patients compliance will be evaluated.

Following indicators will be applied:

Taking Compliance (CC) reflects relationship between number of the product doses taken within defined period and doses, prescribed by attending physician.

Formula: TC = number of doses taken: number of prescribed doses x 100%.

Timing Compliance (TiC).

Formula: TC = number of doses taken in the right time: number of prescribed doses x 100%.

Data would not be taken into consideration when “Product receiving compliance” indicator is less than 90%, and “Accuracy compliance” is less than 90%.

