4.5.3.6 Unplanned visit

If patient prematurely withdraws from the study at any stage, it is required, if possible, to perform all procedures associated to premature withdrawal from the study visit within one week following decision of patient withdrawal. Procedures of this visit are identical to the procedures of the end of treatment visit (Visit 6).

Table 5 Timetable of basic procedures of the study

	Visit 1	Visit 2	Visit 3 (2 weeks ± 3 days)	Visit 4 (4 weeks ± 3 days)	Visit 5 (8 weeks ± 3 days)	Visit 6 (12 weeks ± 3 days)	Visit 7 (30 + 5 days after end of treatment)
Days (D)	D from - 14	D1	D15 (±3)	D29 (±3)	D57 (±3)	D85 (±3)	D114 -
Reception of the informed consent	X						
Demographic data ¹ /patient history acquirement	X						
Previous and concomitant therapy assessment	X	X	X	X	X	X	X
Assessment and registration of AE	X	X	X	X	X	X	X
Physical examination ²	X	X	X	X	X	X	X ³
Complete blood count ⁴	X				X	X	
Blood chemistry ⁵	X				X	X	
Urinalysis ⁶	X				X	X	
Serological examination (HIV, Hep B and C)	X						
PSA level assessment (male only)	X						
Pregnancy test (only women with child-bearing potential)	X	X				X	

US-examination of kidneys, bladder and urine excretory ways (residual urine volume assessment)	X						
US examination of the bladder with residual urine volume assessment		X		X	X	X	
Cough probe	X						
12-lead ECG	X					X	
Assessment with OAB Awareness Tool Questionnaire	X	X	X	X	X	X	
Quality of Life assessment with EQ5D Questionnaire		X				X	
Issue/return and assessment of the diary	X	X	X	X	X	X	
Randomization		X					
Study product issue:		X	X	X	X		
Study product return, compliance assessment			X	X	X	X	

¹ Sex, date of birth, race, body mass, height

²Physical examination includes vital parameters assessment

³Is not conducted in case of telephone contact with the patient

⁴Hemoglobin, hematocrit, white blood cells and differential blood count, platelets.

⁵ ALT, AST, bilirubin, creatinine, total protein, glucose, alkaline phosphatase, cholesterol, potassium, sodium

⁶ Specific gravity, pH, protein, urinary sediment

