5.4 Follow up observation of the patients withdrawn from the study

If patient withdraws from center prematurely it is required to ask him to visit center and, if possible, to complete all visit procedures of the end of the study (Visit 6, Week 12).

Investigator should designate the reason for preterm withdrawal in primary documents and CRF. Whether patient is willing to withdraw from the study of one's own free will, Investigator should try to reveal the reason for his/her decision. If preterm withdrawal is associated with adverse event, Investigator should apply all possible efforts for collection of information concerning his/her outcome and record this information in CRF in adverse events section. If withdrawal from the study is secondary to serious adverse event (SAE), immediate notification of Sponsor about SAE procedure should be followed.

Patients, prematurely withdrawn from the study after the start of receiving of the study therapy, will not be substituted by new patients, and their data will be taken into consideration during final assessment.

When patient withdraws from the study due to SAE, patients is observed during the whole period up to resolution of SAE.

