7 EFFICIENCY ASSESSMENT

7.1 Set of efficiency parameters:

Primary efficiency criteria:

Change of mean daily number of urination episodes at the 12 week Visit against the Visit of starting therapy.

Secondary efficiency criteria:

- 1) Change of mean daily number of urinary incontinence episodes at the 12 week Visit against the Visit of starting therapy.
- 2) Change of mean daily number of urinary incontinence episodes during daytime (from 7 am to 11 pm) at the 12 week Visit against the Visit of starting therapy.
- 3) Change of mean daily number of urinary incontinence episodes during nighttime (from 11 pm to 7 am) at the 12 week Visit against the Visit of starting therapy.
- 4) Change of mean daily, mean daytime and mean nighttime number of urinary incontinence episodes at the weeks 2, 4, 8 Visits against the Visit of starting therapy.
- 5) Change of mean number of urinary incontinence episodes per week at the 12 week Visit against the Visit of starting therapy.
- 6) Change of mean daily number of urinary incontinence episodes at the weeks 2, 4, 8 Visits against the Visit of starting therapy.
- 7) Changes in overactive bladder symptoms assessment parameters according to Overactive bladder Awareness Tool Questionnaire at Visits 2, 4, 8 and 12 weeks in comparison to the visit before the beginning of therapy.
- 8) Change of quality of life assessment using EQ-5D questionnaire (at the 12 week Visit against the Visit of starting therapy).

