9.2 Patient population justification

H_0 (null hypothesis): effect of Urotol (tolterodine) according to assessment of mean daily urination episodes exceeds effect of Uritos[®] (Imidafenacin) with non inferiority threshold 0.8 episodes per day.

H_1 (alternative hypothesis): effect of Uritos[®] (Imidafenacin) according to assessment of mean daily urination episodes exceeds effect of Urotol (tolterodine) with non inferiority threshold 0.8 episodes per day.

$H_0: \mu_A - \mu_B \geq \delta$ $H_1: \mu_A - \mu_B < \delta$,

where μ_A, μ_B – efficiency of medicinal products Uritos[®] (Imidafenacin) and Urotol (tolterodine), respectively; δ – non-inferiority threshold ($\delta = 0,8$ episodes per day)

Following levels of error of the first kind = 0.025 and error of the second kind = 0.2 were taken for calculation of the study sample (that corresponds to 80% power of the study), acceptable non-inferiority threshold at the primary endpoint at Week 12 - 0.8 episodes per day; based on results of previous examination of imidafenacin, standard deviation at the primary endpoint is considered to be 2.12 episodes per day on sample consisting from 355 patients.

Sample size calculation is based on formula from [36]:

$$n_A = \frac{(r+1)\sigma^2(Z_{1-\beta} + Z_{1-\alpha})^2}{r((\mu_A - \mu_B) - \delta)^2}$$

Where $r = n_A/n_B$,

σ – assumed standard deviation for change in mean daily number of urination episodes.

n_A, n_B – study group and control group sizes, respectively.

μ_A, μ_B – assumed mean change of mean daily urination episodes in study group and control group, respectively.

$Z_{1-\alpha}, Z_{1-\beta}$ – cumulative function parameters of normal standard distribution for first (α) and second (β) types of errors, respectively.

δ – non-inferiority threshold.

With due consideration of homogeneous distribution of patients among treatment groups ($n_A = n_B$ if $r = 1$), in each treatment group will be randomized

$$n = \frac{2 \cdot 2.12^2 (0.84 + 1.96)^2}{0.02} = 111$$

Sample containing 222 patients (111 per study group) is considered to be sufficient for proof of alternative hypothesis (rejection of null-hypothesis) at the significance level 0.025% and study strength 80%. With due consideration of withdrawal during treatment total amount of patients to be randomized is about 300 (150 patients per study group).

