9.7 Patients selection for assessment

Efficiency analysis will be performed on FAS population (Full Analysis Set), including all randomized patients taken at least one dose of the study product and having at least one efficiency assessment after Visit 2. Efficiency analysis in this population will be performed according to the assigned treatment.

Per protocol population (PP) includes all FAS population patients, went through all planned visits up to Visit 6, observing protocol conditions, namely patients, eligible to inclusion/non-inclusion criteria and finished participation in the study in accordance with all protocol requirements (except slight deviations from the protocol, which are not a cause for withdrawal from the study). Efficiency analysis in this population will be performed for confirmation of the

conclusions, obtained after efficiency assessment in FAS population.

List of major deviations from the protocol, caused patient withdrawal from the study or from PP population during statistical analysis, will be finalized by Sponsor before completion of statistical analysis and consequently will be presented in final study report. These protocol deviations may include but not limited to the following:

- Non-compliance with inclusion or non-inclusion criteria by the patient participating in the study.
- Participation of the patient in the study having exclusion criteria according to the study protocol;
- Incorrect study product administration schedule and dosage;
- Administration of the medicines, forbidden by the protocol

All randomized patients, receiving test product/comparator product, at least once, will constitute population for safety assessment. Safety assessment will be performed based on the actual treatment received by the patients. All AE revealed during the study should be included into analysis.

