9.8 Efficiency assessment

Efficiency assessment of mean daily, mean daytime and mean nighttime number of urinary incontinence episodes / urination at the Week 2, 4, 8 and 12 Visits, including analysis based on primary efficiency criteria, as well as mean number of urinary incontinence episodes per week at the Week 12 – will be performed with the use of covariance analysis (ANCOVA). Number of urinary incontinence episodes / urination at the Visit of start of therapy will be used as covariate, and therapy group will be used as factor. Primary efficiency analysis according to primary efficiency criteria will be performed in FAS and PP populations. For evaluation of hypothesis of “non-inferior” efficiency upper border of one-side 95% confidence interval for difference in evaluation of mean daily number of urinations among test product and control product tolterone will be calculated. During comparison of therapy groups according to other efficiency criteria two-sided 95% confidence intervals will be built. Comparison of therapy groups on efficiency criteria: change in Overactive Bladder Awareness Tool Questionnaire (OAB Awareness Tool) and change in Quality of life by Quality of life Questionnaire EQ-5D will be performed following data validation concerning their normality, distribution using Kolmogorov-Smirnov criteria. In case of normal distribution data will be compared using Student’s t-test, otherwise non-parametric Mann-Whitney criteria will be used.

Primary efficiency analysis according to secondary efficiency criteria will be performed in FAS and PP populations.

Kolmogorov-Smirnov test for normal distribution and heterogeneous dispersion test using Leven criteria will be also performed during every visit as additional assessments in FAS population for mean daily, mean daytime and mean nighttime number of urinations and urinary incontinence episodes at Weeks 2, 4, 8 and 12. In case when one of these tests is apparently statistically significant ($p < 0.05$), comparison between therapy groups will be performed using non-parametric Mann-Whitney criteria.

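### Early stoppers belong to the FAS but add nothing to the Week 12 primary estimate, so the FAS result is in effect a completer analysis and no planned analysis tests the effect of dropout

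*Combined protocol and SAP*

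**What the plan says.** - **Endpoint (7.1):** "Change of mean daily number of urination episodes at the 12 week Visit against the Visit of starting therapy".
- **FAS (9.7):** "including all randomized patients taken at least one dose of the study product and having at least one efficiency assessment after Visit 2". No Week 12 value is required.
- **Per-protocol set (9.7):** FAS patients who "went through all planned visits up to Visit 6" and kept to the protocol. This analysis is meant to confirm the FAS conclusion.
- **Model (9.8):** an ANCOVA in which the count "at the Visit of start of therapy will be used as covariate, and therapy group will be used as factor". No visit term, subject effect or repeated-measures structure is named.
- **Missing data (9.5):** "Missing, non-assessable and equivocal data will not be substituted and considered to the frames of statistical analysis of the results". The English is awkward, but it rules out imputation. No missing-data sensitivity analysis appears anywhere.
- **Withdrawn patients (5.4):** they "will not be substituted by new patients, and their data will be taken into consideration during final assessment". No method is given.
- **Closing visit (4.5.3.6):** sites should, if possible, "perform all procedures associated to premature withdrawal from the study visit within one week following decision of patient withdrawal". The procedures are those of Visit 6, and 5.4 labels them as Visit 6, Week 12.
- **Diary mean (7.2):** episodes between two visits divided by the days between them.

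**The concern.** The FAS is meant to represent the patients as randomised, and 5.4 says that withdrawn patients will count. Under 9.5 and 9.8 they do not count for the primary endpoint. Their Week 2, 4 and 8 diary means feed only secondary comparisons at those visits.

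This matters in a non-inferiority trial. The treatment is open-label (4.3.2), so patients and investigators know the product when they decide whether to stop. If reasons for stopping differ between arms, the Week 12 completers may no longer be comparable. The FAS and per-protocol estimates would share that distortion, and agreement between them would not show that it is absent.

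The closing visit adds a second uncertainty. Two statisticians could follow the same text and differ on whether its diary mean is a Week 12 value. That mean may include days after the last dose.

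**Working it through.** **1. Trace one patient.** A patient stops at Week 5 with Week 2 and Week 4 diary means.
- In the FAS under 9.7: yes.
- Week 12 value: none, unless the closing visit is counted as one.
- Substituted under 9.5: no.
- In the Week 12 ANCOVA: no.
- In the per-protocol set: no.

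A patient with no assessment after Visit 2 leaves the FAS altogether.

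**2. Reproduce the sample size (9.2).** Inputs: SD 2.12, margin 0.8, assumed true difference 0 (the plan states none, and 0 reproduces its figure). On the error rates: "Following levels of error of the first kind = 0.025 and error of the second kind = 0.2 were taken".

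n per arm = 2 × 2.12² × (0.84 + 1.96)² / 0.8² = 110.1, rounded up to 111, or 222 in total. This matches the plan. The printed denominator of 0.02 would give about 3,524 per arm, so I read it as a printing fault for 0.64.

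Allowance for loss = (300 − 222)/300 = 26%, or 39 per arm. The 80% power thus rests on the number of completers. Power is 80.3% with 111 per arm, and would be 90.5% if all 150 per arm gave full Week 12 information.

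**3. How far dropout can move the result.** Differences are test minus control in change, so positive values are against the test product. Suppose the true difference over all randomised patients is exactly 0.8, a fraction d is lost in each arm, and the difference among dropouts exceeds that among completers by Δ. Then:

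- completer difference c = 0.8 − dΔ
- SE = 2.12 × √(2 / [150(1 − d)])
- P(non-inferiority declared) = Φ((0.8 − c)/SE − 1.96)

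| d | SE | Δ | c | P |
|---|---|---|---|---|
| 26% | 0.285 | 0 | 0.80 | 2.5% |
| 26% | 0.285 | +0.5 | 0.67 | 6.6% |
| 26% | 0.285 | +1.0 | 0.54 | 14.8% |
| 26% | 0.285 | +2.0 | 0.28 | 44.7% |
| 26% | 0.285 | −1.0 | 1.06 | 0.2% |
| 10% | 0.258 | +1.0 | 0.70 | 5.8% |
| 3% | 0.249 | +1.0 | 0.77 | 3.3% |

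Δ is an assumption; the documents give no value or sign.

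**4. Simulation with an explicit dropout mechanism.** Assumptions: 150 per arm, SD 2.12, true difference 0.8, visit correlation 0.5 to 0.7, dropout depending on the last observed diary value.

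| Dropout depends on response in | Loss | Completer difference | False non-inferiority |
|---|---|---|---|
| Test arm only | 26% | 0.67 to 0.45 | about 7% to 24% |
| Both arms alike | 26% | about 0.8 | about 2.5% |
| Control arm only | 26% | about 1.0 to 1.2 | near 0% |
| Test arm only | 10% | – | about 4% to 8% |
| Test arm only | 3% | – | about 3% |

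The upper end depends on the assumed strength: odds ratios of about 1.65 and 2.7 per SD gave 7.7% to 25.6% in a separate run. A likelihood analysis using Weeks 2, 4 and 8 returned 0.80 and about 2.5%. With purely random 26% dropout it cut the standard error by about 4% to 6%.

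**The case against.** **Loss may be small.** A reader might infer that the plan expects 26% to drop out. It does not: it randomises about 300 to secure at least 222, which is an allowance. The imidafenacin studies in 2.2.6 show far less loss. Table 3 has 364 cases at baseline and 355 at Week 12 (9/364 = 2.5%), and Table 4 has 159 of 159, though that may be a selected cohort. Section 2.4 reports no withdrawal for dry mouth at 0.2 mg/day, with no figure for tolterodine. This stands, and it limits the size of the problem.

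**The bias need not favour the test product.** That inference is tempting in an open-label non-inferiority trial. It needs dropout that depends on response in the test arm and not in the control arm, and nothing in the documents supports that asymmetry. This stands.

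**The likelihood result is built in.** The simulated dropout depends only on observed values, so it is missing at random by construction. Recovering 0.80 says nothing about dropout driven by unobserved response. This also stands.

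**Withdrawn patients are brought back.** Sections 4.5.3.6 and 5.4 do ask for a closing visit, and a reader might infer that an early off-drug mean will be analysed as Week 12. No rule says so, and none excludes it. Carrying such a value to Week 12 would also sit badly with 9.5. What can be supported is that the sections are unreconciled.

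**Per-protocol analysis is not redundant.** The FAS keeps Week 12 completers with major deviations and the per-protocol set removes them. That tests deviations, not dropout.

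**Conclusion.** The point holds. Under 9.5, 9.7 and 9.8 together, the FAS primary result is in effect a Week 12 completer analysis. The statement in 5.4 about withdrawn patients' data has no method behind it for the primary endpoint, and the status of the closing visit is undefined. That each visit is modelled separately is inferred from the terms named in 9.8; the plan does not say it outright.

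The size is conditional. Under the step 4 assumptions, the error rate at the full allowance runs from near 0% to about 24%, depending on which arm's dropout follows response. At the loss seen in the earlier 52-week study it barely moves from 2.5%. The documents do not support a claim that the trial is biased towards non-inferiority. They support a narrower one: the plan discards relevant data it already collects and has no analysis that would show whether dropout mattered.

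The sample size need not change. These figures use the one-sided 0.025 level of 9.2 and 9.3; the one-sided 95% interval in 9.8 is a separate inconsistency.

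**What to change.** - **9.8:** make the FAS primary analysis a mixed model for repeated measures on the Week 2, 4, 8 and 12 changes, with treatment, visit, treatment-by-visit, baseline, baseline-by-visit and unstructured covariance. Compare the upper bound of the Week 12 contrast with 0.8.
- **Sensitivity analyses:** keep the Week 12 ANCOVA and add one missing-not-at-random check, such as a delta-adjusted tipping point.
- **4.5.3.6 and 5.4:** label the closing visit *early termination* and record the last-dose date.
- **7.2:** assign diary days to visit windows by study day, so that earlier days never count as Week 12.
- **9.5:** align it with these changes. State also whether its 90% compliance exclusion applies to the FAS, since it is not limited to the per-protocol set and could remove further data.

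The cost is analysis-plan wording, one eCRF visit label and slightly more programming. No extra patients, visits or diary data are needed. The downside is reliance on missing at random, which is weaker than the assumption the completer analysis needs and which the tipping-point check would probe.

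### The 90% compliance rule in section 9.5 names no analysis set and no counting period; applied as written, it removes patients from the FAS primary analysis, against section 9.7

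*Combined protocol and SAP*

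**What the plan says.** Section 9.5 puts a compliance check ahead of the analysis: "Before taking decision concerning inclusion of data, obtained during clinical study, into assessment, patients compliance will be evaluated". It then defines two indicators. Taking Compliance relates "number of the product doses taken within defined period and doses, prescribed by attending physician"; Timing Compliance is "number of doses taken in the right time: number of prescribed doses x 100" per cent. The exclusion rule follows: "Data would not be taken into consideration when “Product receiving compliance” indicator is less than 90%, and “Accuracy compliance” is less than 90" per cent. The two names in that sentence are not the two just defined. The rule speaks of data rather than patients, and it names no analysis set. The period for counting doses is called defined, but neither 9.5 nor any other section defines it.

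Section 9.7 defines the FAS as "including all randomized patients taken at least one dose of the study product and having at least one efficiency assessment after Visit 2" and adds: "Efficiency analysis in this population will be performed according to the assigned treatment". It sets no compliance condition. Among the deviations that can lead to withdrawal from the study or from PP it lists "Incorrect study product administration schedule and dosage", with no percentage and no reference to 9.5. The PP analysis is there to confirm the FAS conclusions, and section 9.8 runs the primary analysis in both sets.

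Two other sections bear on the rule. Section 6.3 gives a similar ratio, actual over scheduled administrations, and calls 95% or more satisfactory, with no period and no consequence for the analysis. Section 5.4 says that patients who withdraw after starting therapy are not replaced and that their data still count in the final assessment.

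**The concern.** Compliance is observed after randomisation and can depend on tolerability and response, so removing patients because of it breaks the comparison that randomisation set up. Such a restriction belongs in a PP analysis. Section 9.5 places it before any data enter the assessment, which covers the FAS as well. For a FAS patient below 90%, 9.5 says leave the data out and 9.7 says analyse the patient as assigned; both cannot be followed.

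At stake is who is in the primary non-inferiority analysis. If the rule reaches both sets, the FAS also moves towards the PP set, and a PP analysis meant to confirm the FAS result tells the reader less. The undefined denominator adds a second uncertainty, because the same patient can fall on either side of 90% depending on how doses are counted.

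**Working it through.** The plan gives no non-compliance rate and no worked compliance figure, so there is none to reproduce. The check has a textual part and a dose-counting part.

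**1. Scope, section against section.**
- 9.5: compliance is assessed before data are included; data below 90% are left out; no set is named.
- 9.7, FAS: one dose and one assessment after Visit 2; analysed as assigned; no compliance condition.
- 9.7, PP: incorrect schedule and dosage is a listed deviation; no threshold; no link to 9.5.
- 9.8: primary analysis in FAS and PP.

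Nothing limits the 9.5 rule to PP.

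**2. What the joint condition does.** Let P be doses prescribed, T doses taken and O doses taken on time. Then O ≤ T, so O/P ≤ T/P. If T/P is below 90%, O/P must be too. Requiring both to be below 90% is therefore the same as requiring Taking Compliance below 90%, and the timing indicator never changes who is excluded. If either were enough, the test would reduce to Timing Compliance alone and could exclude more patients.

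**3. Whole-course threshold.** Inputs: 84 days of therapy (section 4.5), two doses a day (section 6.1).
- Planned doses: 84 × 2 = 168.
- 90% level: 0.90 × 168 = 151.2. So 151/168 = 89.9% is excluded and 152/168 = 90.5% is kept: 17 or more missed doses exclude.
- 95% level in 6.3: 0.95 × 168 = 159.6, so 159/168 = 94.6% is not satisfactory: 9 or more missed.

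A patient who misses 9 to 16 doses is thus unsatisfactory under 6.3 but retained under 9.5, and the plan does not say how the two levels relate.

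**4. Denominator for a patient who withdraws.** Take a patient who misses no dose until stopping (14 doses a week).

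| Stops at | Against 168 planned doses | Against doses due |
|---|---|---|
| Week 8 | 112/168 = 66.7% | 112/112 = 100% |
| Week 10 | 140/168 = 83.3% | 140/140 = 100% |
| Week 11 | 154/168 = 91.7% | 154/154 = 100% |

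Against planned doses, anyone who stops after 75 or fewer days is below 90% (150/168 = 89.3%), while 76 days passes (152/168 = 90.5%). The plan allows for 300 − 222 = 78 patients lost (26%). The documents do not say when they would be lost. If withdrawals were spread evenly over the 84 days, an assumption, 75/84 = 89% of them would fall below the threshold; the possible range is from none (all stop after day 75) to all. Some would not be in the FAS anyway, for want of an assessment after Visit 2.

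**5. Counting by interval.** Days 57 to 84 (Visit 5 to Visit 6) hold 28 × 2 = 56 doses. A patient who misses six doses, all in that interval, scores 50/56 = 89.3% by interval and 162/168 = 96.4% over the course. The first would exclude, the second would not.

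**The case against.** The strongest reply is that the specific section governs the general one. Section 9.7 is where populations are defined, it gives the FAS no compliance condition, and it treats incorrect schedule and dosage as a PP matter. On that view 9.5 merely supplies the number for that PP deviation. This is plausible and probably what was meant. But 9.5 does not refer to PP and 9.7 does not refer to 9.5, so a statistician who applies 9.5 as written does nothing the text forbids.

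Other points on that side stand in part:
- Section 9.5 speaks of each patient's compliance and of data from the whole study, so one figure per patient is the more natural count. Visit-by-visit issue and return of drug is accountability. The interval count is not excluded, but it is the weaker reading.
- Under the joint condition the redundant timing indicator changes nobody's status, and the mismatched names may be translation. Both are drafting faults.
- Section 5.4 names no efficacy set, so its relation to 9.5 is a tension and not a contradiction. Section 9.5 also says "Missing, non-assessable and equivocal data will not be substituted"; a patient who withdraws without a week 12 value adds nothing to the week 12 comparison under any denominator.
- The report duty in 9.5 and the amendment clause in 9.6 would disclose a choice, but they do not settle which rule applies.

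A reader might infer two stronger things. One is that the sponsor could set FAS membership after seeing data by arm, because the trial is open-label and 9.7 has the deviation list finalised before the analysis is completed. That clause governs deviations that lead to withdrawal from the study or from PP; it does not govern the FAS or the 9.5 threshold, which is prespecified. The other is that the rule favours non-inferiority. The documents give neither the share of patients below 90% in each arm nor how such patients respond, and moving the FAS towards PP is not in itself anti-conservative in a non-inferiority trial.

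**Conclusion.** The concern holds and should be fixed before the analysis. As written, 9.5 takes patients below 90%, or their data, out of the FAS primary analysis on a post-randomisation variable, and this conflicts with 9.7. The PP-only reading is reasonable but unstated. The conflict rests on the text alone and needs no numerical assumption.

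The undefined period and denominator are a second, real gap: 66.7% or 100% for the same fully compliant patient who stops at week 8, and, on the less natural interval reading, 89.3% or 96.4% for a patient with six late misses. For the week 12 comparison, the patients at risk of removal are those with a week 12 value who fall below 90%, which over the planned course means 17 or more missed doses. The documents do not say how many there would be, so neither the size nor the direction of any bias can be stated.

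**What to change.** 1. State in 9.5 that the 90% rule defines a PP exclusion only, and that the FAS keeps every patient who meets the 9.7 definition, as assigned, regardless of compliance. Refer to the rule from the PP deviation list in 9.7.
2. State one counting period and one denominator, including for patients who withdraw. Use the defined names, Taking Compliance and Timing Compliance. Say whether both or either must be below 90%, knowing that the timing indicator has no effect if both are required. State how the 90% relates to the 95% satisfactory level in 6.3.
3. Fix the PP exclusion list before the analysis starts. Once the rule sits in PP, this list decides who is in the confirming analysis, and the trial is open-label.

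The cost is a protocol amendment on wording. No new data are needed: dosing is already recorded in the diary and drug is already counted on return.
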